#### **5.3.1.2 Confinement**

Subjects will not be confined in this study.

#### **5.3.1.3 Meals and Dietary Requirements**

There are no meal and dietary requirements for this study.

#### **5.3.1.4 Blood Samples for Pharmacogenetic Analysis**

One 4 mL whole blood sample for DNA isolation will be collected on Cycle 1 Day -2 from each subject who consents to provide a sample for pharmacogenetic analysis. The procedure for obtaining and documenting informed consent is discussed in Section 9.3. If

the sample is not collected on Cycle 1 Day –2, it may be collected at any time throughout the study.

The sample collection tubes will minimally be labeled with "PG-DNA," protocol number, and subject number. Samples will be shipped frozen to AbbVie or a designated laboratory for DNA extraction and long-term storage. Instructions for the preparation and shipment of pharmacogenetic samples will be provided in the study specific laboratory manual.

If pharmacogenetic (PG) testing is performed, results from individual subjects will be kept coded and confidential and will not be given to anyone not directly involved with this research study. AbbVie will store the DNA samples in a secure storage space with adequate measures to protect confidentiality. Samples will be coded so that subject identities will not be available to the scientists conducting the genotyping analyses. Individual subject results will not be provided to the Investigator so that neither the subject nor the Investigator will have knowledge of specific subject genotypes. AbbVie will keep the DNA samples until destroyed by AbbVie when this research is completed. These samples will not be stored longer than 20 years or per country requirement.

### **5.3.1.5 Collection and Handling of Pharmacodynamic Variables**

Pharmacodynamic correlative studies are exploratory in nature. Serum, plasma and tissue specimens may be utilized to evaluate known and novel markers (nucleic acids, peptides/proteins and/or metabolites) of disease status. PD variables will be further discussed in Section [5.3.7](#).

#### **Blood Collection for Plasma Markers**

Twelve (12) mL (Cycle 1 Day –2 or Final Visit) or 6 mL (all other time points) of blood will be collected pre-dose by venipuncture at time points outlined in [Table 9](#) in conjunction with PK samples, if possible. The collection, processing and storage should be performed as described in the study specific laboratory manual. The complete process of centrifugation, transfer to cryovial and freezing should be accomplished in less than 1 hour from the time of blood draw.

### **Blood Collection for Serum Markers**

Approximately 5 mL of blood will be collected pre-dose by venipuncture at time points as outlined in [Table 9](#). The collection, processing and storage should be performed as described in the study specific laboratory manual. The complete process of clot formation, centrifugation, transfer to cryovials and freezing should be accomplished in less than 90 minutes from the time of blood draw.

### **Tissue Collection for IHC, ELISA and FISH DNA Mutational/Methylation Analysis**

#### **Archived Tissue Specimens:**

Subjects must consent to provide available archived tissue for analysis. It is recognized that samples suitable for analysis will not be available from all consenting subjects. The most recent archived biopsy is preferred and should be obtained at Cycle 1 Day -2, if possible. While sending FFPE blocks is preferred, slides prepared by the local pathology laboratory are acceptable and should be prepared as described in the study specific laboratory manual. Study specific biopsies are not required for subject participation.

#### **5.3.1.6 Shipment of Pharmacodynamic Samples**

All samples should be labeled and shipped as outlined in the study specific laboratory manual. An inventory of the samples being shipped will accompany the package.

#### **5.3.2 Drug Concentration Measurements**

##### **5.3.2.1 Collection of Samples for Analysis**

#### **Blood Samples for Veliparib Assay**

Blood samples for veliparib assay will be collected by venipuncture at the designated time points outlined in [Table 10](#) (Phase 1) and [Table 11](#) (Phase 2). The timing of blood collection is fundamental to the success of the study. The timing of blood collections will take priority over all other scheduled study activities except for dosing. The order of blood collections will be maintained to the minute such that the time intervals relative to

the preceding dose will be the same for all subjects. The time that each blood sample is collected will be recorded to the minute.

The date and time of the morning dose of veliparib on PK sampling day will be recorded. In Phase 2 portion, the date and time of the two doses of veliparib prior to PK sampling on C1D1, C2D1, C3D1 and C4D1 will also be recorded.

The collection, processing and storage should be performed as described in the study specific laboratory manual.

Approximately 7 blood samples are planned to be collected per subject in Phase 1 and 6 samples per subject in Phase 2 for pharmacokinetic analysis. The approximate number of blood samples planned for pharmacokinetic analysis is approximately 1325 for the entire study.

#### **Blood Samples for Etoposide Assay**

Blood samples for etoposide assay will be collected at the time points specified in [Table 10](#). The date and time of the dose of etoposide on PK sampling day will be recorded. The collection, processing and storage should be performed as described in the study specific laboratory manual. A total of 10 samples per subject will be collected for etoposide analysis in Phase 1 Cycles 1 and 2. Blood samples for etoposide assay will not be collected for Phase 2 subjects.

#### **Blood Samples for Unbound Carboplatin Assay**

Plasma concentration-time course of carboplatin will be determined on Cycle 1 Day 1. Blood samples will be collected at the time points outlined in [Table 10](#). The date and time of the dose of carboplatin on PK sampling day will be recorded. The collection, processing and storage should be performed as described in the study specific laboratory manual. A total of 3 samples per subject will be collected for carboplatin assay in Phase 1 Cycle 1 Day 1. Blood samples for carboplatin assay will not be collected for Phase 2 subjects.

Pharmacokinetic variables are discussed in Section 5.3.5.

#### **5.3.2.2 Handling/Processing of Samples**

The processing and storage of the PK samples for veliparib, carboplatin and etoposide should be performed as described in the study specific laboratory manual.

AbbVie or a designated laboratory will store the pharmacokinetic samples in a secure storage space with adequate measures to protect confidentiality. To increase confidence in trends, remaining sample aliquots may be used to perform replicate tests, or sample analysis at additional time points for tests currently identified in the protocol. The placebo samples may not be analyzed to confirm the absence of veliparib. Upon completion of this research, AbbVie or a designated laboratory will destroy the samples.

#### **5.3.2.3 Disposition of Samples**

The frozen plasma samples for veliparib, carboplatin and etoposide assays will be packed in dry ice sufficient to last during transport and shipped from the study site to the central laboratory according to instructions in the central laboratory manual.

#### **5.3.2.4 Measurement Methods**

##### **Analysis of Plasma Samples**

Plasma concentrations of veliparib will be determined under the supervision of the Drug Analysis Department at AbbVie. Placebo samples may or may not be analyzed to confirm the absence of veliparib (ABT-888). Plasma concentrations of etoposide and carboplatin will be determined at external laboratories using validated assays under the supervision of the Drug Analysis Department at AbbVie.

#### **5.3.3 Efficacy Variables**

Efficacy variables are not primary endpoints in the Phase 1 Dose Escalation portion of the study.

The primary efficacy endpoint in Phase 2 is progression free survival (PFS) from the time of subject randomization. The secondary endpoints are objective response rate (ORR), overall survival (OS). The tertiary endpoints are duration of response (DOR) and ECOG performance status.

### **5.3.3.1 RECIST 1.1 for Tumor Response**

Response criteria will be assessed using RECIST (Version 1.1). Changes in the measurable lesions over the course of therapy must be evaluated using the criteria presented in [Appendix C](#). Tumor assessments will be performed until disease progression. See tumor assessment schedule in Section [5.3.1.1](#).

### **5.3.3.2 Definition of Disease Progression**

Disease progression will be defined as radiographic progression of disease as determined by the investigator by RECIST (Version 1.1) [Appendix C](#).

Clinical progression as determined by the investigator, which may be characterized as, but not limited to:

- Increase in at least two points of ECOG performance status attributable to cancer progression;
- Subject requires non-palliative radiation, chemotherapy or surgery due to progressive disease;
- Death from progressive disease.

In cases where an Investigator determines that a subject has met the criteria for clinical disease progression, every effort should be made to confirm the progression radiographically.

### **5.3.4 Safety Variables**

AbbVie will assess adverse events, laboratory data, ECGs and vital signs throughout the study. Adverse events intensity and laboratory evaluation changes will be assessed by utilizing NCI CTCAE Version 4.0.

During the conduct of the study, the AbbVie medical and safety team will be monitoring blinded, subject laboratory results and serious adverse event data as they are reported.

### **5.3.5 Pharmacokinetic Variables**

Values for pharmacokinetic parameters of veliparib, including the maximum observed plasma concentration ( $C_{max}$ ), the time to  $C_{max}$  (peak time,  $T_{max}$ ), the area under the plasma concentration-time curve from time 0 to time of last measurable concentration ( $AUC_t$ ) will be determined for veliparib doses on Day 1 of Cycle 1 using non-compartmental methods.

Values for pharmacokinetic parameters of etoposide including  $C_{max}$ , AUC from time 0 to the last measurable concentration ( $AUC_t$ ) and from time 0 to time infinity ( $AUC_{\infty}$ ), clearance and terminal half-life will be determined on Day 1 of Cycle 1 and Day 1 of Cycle 2 using noncompartmental methods.

Values for compartmental pharmacokinetic parameters of carboplatin in the dose escalation cohorts (such as volume of distribution and clearance) and of veliparib in the Phase 2 part of the study such as rate of absorption ( $K_a$ ), apparent volume of distribution ( $V/F$ ) and oral clearance ( $CL/F$ ) may be estimated using a nonlinear mixed-effect population modeling approach with NONMEM software and reported in a separate pharmacokinetic report.

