### **3.3.2 Veliparib Pharmacokinetics/Pharmacodynamics**

In humans, at least 90% of the dose is absorbed after oral administration of veliparib. Veliparib is primarily cleared in the urine as intact parent drug (73% of administered dose), with a small fraction of clearance from metabolism. Preliminary clinical pharmacokinetic (PK) data available from 6 studies indicate that exposure of veliparib is approximately dose proportional over 10 through 500 mg BID dose range. The absorption of veliparib after oral dosing is rapid, and veliparib plasma concentrations peak at approximately 1 to 2 hours after dosing across dose levels. The terminal half-life of veliparib is about 6 hours, with minimal accumulation following multiple BID dosing. Food does not have a significant effect on veliparib bioavailability.

Veliparib is not a potent inhibitor, nor an inducer, of the major human cytochrome P450s (CYPs), suggesting a minimal potential for DDIs at the anticipated therapeutic concentrations. In study subjects, there was no significant pharmacokinetic interaction between veliparib and TMZ, and preliminary results indicate the absence of DDI between

veliparib and carboplatin/gemcitabine, between veliparib and FOLFIRI, between veliparib and carboplatin/paclitaxel, or between veliparib and capecitabine/5-FU.

In Phase 0 Study A10-161, substantial inhibition of PARP activity was observed in tumor biopsies collected 3 to 6 hours after dosing in all 3 subjects who received a single dose of 25 mg veliparib (92%, 95%, and 100%). For subjects receiving 50 mg, PARP activity inhibition in tumor biopsies averaged 75% at 3 to 6 hours after dosing (N = 3) and averaged 74% at 24 hours after dosing (N = 3). Therefore, both 25 mg and 50 mg veliparib doses were biologically active.

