**Table 10. Schedule of Pharmacokinetic Assessments for Phase 1 Dose Escalation**

Procedure	Visit Schedule	Before Drug Administration	After Drug Administration	Sampling Plan	
				Specimen Matrix	Specimen Matrix
PK Blood Sampling a Etoposide	Cycle 1 Day 1		55 min (5 min before the end of infusion), 3 h, 5 h, 8 h, and 24 h post Day 1 dosing (24 hours is prior to dosing on Cycle 1 Day 2)	Blood → Plasma Frozen -20°C or Colder	Blood → Plasma Frozen -20°C or Colder
PK Blood Sampling a Carboplatin	Cycle 2 Day 1 b Cycle 1 Day 1		55 min (5 min before the end of infusion), 3 h, 5 h, 8 h, and 24 h post Day 1 dosing (24 hours is prior to dosing on Cycle 2 Day 2) 25 min, 4 h, and 23 h post the start of Day 1 carboplatin infusion	Blood → Plasma Frozen -20°C or Colder	Blood → Plasma Frozen -20°C or Colder
PK Blood Sampling for Veliparib (ABT-888) a	Cycle 1 Day 1	Pre-dose	1 h, 2 h, 3 h, 5 h, 8 h, and 24 h	Blood → Plasma Frozen -20°C or Colder	Blood → Plasma Frozen -20°C or Colder

a. Pharmacokinetic sampling is further discussed in Section 5.3.2.1. Samples will not be drawn during carboplatin and/or etoposide dose delays. All timepoints of etoposide and carboplatin samples are referred to the start of the infusion.

b. This sampling will be omitted for subjects receiving continuous veliparib schedule.

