### **5.5.1.1 Administration of Veliparib/Placebo**

Subjects will self-administer the morning dose of veliparib/placebo and the evening doses of veliparib/placebo approximately 12 hours after the morning dose with or without food in the same calendar day. Veliparib dose should be followed by a glass of water (approx. 240 mL).

It is recommended that if a subject misses a scheduled dose of veliparib/placebo and less than 6 hours have passed since the scheduled dosing time, the dose should be immediately taken. It is recommended that if more than 6 hours have passed since the scheduled dosing time, the subject should not take the missed dose but should wait for the next regularly scheduled dose.

If the subject vomits within 15 minutes of taking veliparib, another dose is to be taken. The dose may only be repeated once. If more than 15 minutes has passed from the time of oral dosing then no additional doses will be taken. The subject is to contact the Investigator if additional veliparib is needed to complete BID dosing through the remainder of the cycle.

Subjects will be provided self-administration instructions and subject dosing cards to record the date and time the veliparib was administered. Subjects will be instructed to store veliparib according to specific directions included in [Table 15](#) in Section [5.5.2.3](#). Subjects should return bottles of veliparib (empty, partially filled or full) and the completed dosing card to the study site prior to each cycle and at the Final Visit.

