## **5.5.5 Selection and Timing of Dose for Each Subject**

### **Phase 1 Dose Escalation**

All Phase 1 subjects will receive veliparib orally. Depending on the dosing schedule assigned, veliparib will be dosed twice a day on Days –2 through 5 (7-day schedule) or Days –2 through 12 (14-day schedule) of 1st, 3rd and 4th 21-day cycles and on Days 2 through 5 or Days 2 through 12 (14-day schedule) of the 2nd 21-day cycle, or on Days –2 through 19 (continuous schedule) of the 21 day Cycles 1 – 4 at a dose level based on the dose escalation cohort assignment. One dose will be taken in the morning and the second dose will be taken in the evening (approximately 12 hours after the morning dose). The morning dose of veliparib should be administered in the clinic prior to etoposide and carboplatin, but after chemotherapy premedications on days when administered with chemotherapy. Premedications may be administered per individual institutional standards.

After the end of Cycle 4, subjects without evidence of disease progression by radiographic assessment (CT) will receive veliparib at 400 mg BID continuous schedule 21 day cycle, until disease progression or unacceptable toxicity.

A "3 + 3" escalation rule will be used for the Phase 1 dose escalation portion of this study, with a condition applied for the Dose Level 1, which will allow 3 additional subjects to be entered in Dose Level 1 if 2 of 6 initial subjects experience DLTs. Enrollment of the 3 additional subjects at all dose levels will depend on a review of the specific DLTs observed and discussion with the Investigators. At the RPTD and schedule, additional subjects will be added as needed so that a total of at least 9 subjects will be treated at the RPTD.

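### Phase 1 veliparib AUCt, as defined, is integrated from 8 h to 24 h across an unsampled evening dose, so the tabulated value is neither a dosing-interval nor a 24 h AUC

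*Protocol*

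**What the plan says.** Protocol Section 5.3.5 lists Cmax, Tmax and AUCt for veliparib on Cycle 1 Day 1, by non-compartmental methods. AUCt is "the area under the plasma concentration-time curve from time 0 to time of last measurable concentration".

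Table 10 schedules Phase 1 veliparib samples pre-dose and at "1 h, 2 h, 3 h, 5 h, 8 h, and 24 h". Section 5.3.2.1 confirms the count: "Approximately 7 blood samples are planned to be collected per subject in Phase 1".

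Section 5.5.1.1 has subjects take "the evening doses of veliparib/placebo approximately 12 hours after the morning dose". Section 5.5.5 repeats this for Phase 1 and starts twice-daily dosing on Day -2. Nothing withholds the evening dose on Cycle 1 Day 1.

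Section 3.3.2 gives the kinetics: "The terminal half-life of veliparib is about 6 hours", a peak at roughly 1 to 2 h, and approximately dose-proportional exposure from 10 to 500 mg twice daily.

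Section 8.1.6.1 tabulates the pharmacokinetic parameters by subject and dose level. Section 8.1.6.2 models dose proportionality on dose-normalised Cmax and AUC0-8, and admits other parameters if the data determine them adequately. AUC0-8 is not named in Section 5.3.5, and AUCt is not named in the dose-proportionality text of Section 8.1.6.2.

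**The concern.** The 24 h sample is a trough after the evening dose. It is not the tail of the morning dose. A trapezoid from 8 h to 24 h treats the two levels as points on one declining curve and omits the evening rise and peak.

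A reader of the tables would naturally take AUCt as exposure over either one 12 h interval or a full day. It is neither, and no passage says how the evening dose is handled. The value also depends on when a self-administered dose was taken. For Phase 1, Section 5.3.2.1 asks only that "The date and time of the morning dose of veliparib on PK sampling day will be recorded"; the evening time is on the subject's dosing card (Section 5.5.1.1).

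**Working it through.** **The plan's own figure.** Section 5.3.2.1 gives about 1325 veliparib samples. 35 × 7 + 180 × 6 = 245 + 1080 = 1325. It reproduces exactly, so the seven Phase 1 samples are those in Table 10 and none falls near the evening peak.

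**Inputs.** Half-life 6 h and Tmax 1 to 2 h (Section 3.3.2); doses at -48, -36, -24, -12, 0 and 12 h (Section 5.5.5); samples at 0, 1, 2, 3, 5, 8 and 24 h (Table 10). Assumptions: one compartment with first-order absorption, evening dose at exactly 12 h, and the 24 h sample drawn before the Day 2 morning dose (Table 10 says this for etoposide but not explicitly for veliparib).

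**Model.** For one dose, c(t) = ka/(ka - k) × (exp(-kt) - exp(-ka t)), in units of dose/volume, with k = ln 2/6 = 0.1155 per h. ka is solved from Tmax = ln(ka/k)/(ka - k). C(t) is the sum over the six doses.

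**Worked case, Tmax 1.5 h (ka = 2.02 per h).** C at 0, 1, 2, 3, 5, 8 and 24 h is 0.352, 1.118, 1.103, 0.996, 0.793, 0.561 and 0.353.

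- Linear trapezoid, 0 to 8 h: 0.735 + 1.111 + 1.050 + 1.789 + 2.031 = 6.715 (from unrounded terms).
- 8 to 24 h: 16 × (0.561 + 0.353)/2 = 7.312. The exact area there is 10.450, so this segment is 30% low.
- AUCt = 6.715 + 7.312 = 14.027, of which 7.312/14.027 = 52% comes from the faulty segment.
- Exact AUC0-24 = 17.301, so AUCt is 14.027/17.301 - 1 = -18.9%.
- Exact AUC0-12 = 8.647, so AUCt is 14.027/8.647 = 1.62 times AUC0-12.
- Exact AUC0-8 = 6.852, so the sampled AUC0-8 is 6.715/6.852 - 1 = -2.0%.

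**All three Tmax values, half-life 6 h, evening dose at 12 h.**

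| Tmax | AUCt vs AUC0-24, linear | linear-up/log-down | AUCt / AUC0-12 (linear; log-down) | AUC0-8 error | AUC0-12 error, 24 h trough placed at 12 h (linear; log-down) |
|---|---|---|---|---|---|
| 1 h | -20.2% | -21.1% | 1.60; 1.58 | -3.3% | -2.2%; -2.9% |
| 1.5 h | -18.9% | -19.8% | 1.62; 1.60 | -2.0% | -1.2%; -1.9% |
| 2 h | -17.7% | -18.6% | 1.65; 1.63 | -1.4% | -0.7%; -1.4% |

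The modelled 24 h level is about 29 to 34% of the peak. No assay limit is stated, but a level that high should be measurable, so the definition runs AUCt to 24 h.

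**Sensitivity.** With half-lives of 5 to 7 h, Tmax 1 to 2 h and the dose at 12 h, AUCt is about 16 to 25% low. With half-life 6 h and the evening dose anywhere from 9 to 14 h, it is about 10 to 30% low; the earlier the dose, the larger the shortfall. The direction is downward in every case.

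**The case against.** The strongest reply is that little depends on this parameter. The formal test in Section 8.1.6.2 uses AUC0-8, which lies within one dosing interval. The Phase 1 pharmacokinetic objective is the interaction with etoposide, and etoposide is infused once per 24 h, so its AUC has no such gap. No passage labels AUCt as a 12 h or 24 h exposure. Under linear kinetics the proportional bias is similar at every dose level, so comparisons between levels change little. All of this stands, and it limits the point to a descriptive table and the optional additional parameters.

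It can also be said that the integration limit may be set elsewhere. SAP Section 4.2 covers Phase 2 only and leaves the pharmacokinetic analysis to a later report appendix, which is not available here. That is possible, but the protocol's definition is explicit and would produce the faulty area if followed.

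Two stronger readings are tempting. A reader might infer that the recommended Phase 2 dose rests on a biased exposure figure. The documents do not support that. Section 5.1 bases it on observed toxicities, the MTD or MAD and overall safety; the synopsis says it was determined from the DLT rate and tolerability; Section 6.8.2 brings in available PK data only if no MTD is reached, and does not name AUCt. A reader might also infer that evening-dose timing dominates AUCt, because a dose at 9 h or 14 h moves the 24 h concentration by about -22% or +19%. AUCt itself moves only about 4% either way if the Day 1 evening dose alone shifts.

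**Conclusion.** The point holds in limited form. That AUCt crosses an unsampled dose follows from the definition, Table 10 and the twice-daily schedule, given a measurable 24 h level. The size is model-based: about 18 to 21% below AUC0-24 and about 1.6 times AUC0-12 under one compartment, half-life 6 h, Tmax 1 to 2 h and an evening dose at 12 h. The wider ranges shown above should accompany any quoted figure.

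What is affected is the AUCt tabulated under Section 8.1.6.1, and any use of it as an additional parameter in Section 8.1.6.2. The planned AUC0-8 test, the etoposide AUC and the basis of the recommended Phase 2 dose are not called into question. The change is still worth making, because the tabulated parameter has no clear interpretation as written and the protocol already uses a sound alternative.

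**What to change.** In Sections 5.3.5 and 8.1.6.1, replace veliparib AUCt with AUC0-8, matching Section 8.1.6.2, and state that veliparib AUC is not integrated past the evening dose. The model error of AUC0-8 with the existing samples is about 1 to 3%.

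Optionally, add AUC0-12 as a secondary parameter. Use the 24 h sample as the steady-state 12 h trough, at the actual time since the evening dose taken from the existing dosing cards. Flag that it relies on self-recorded times.

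The cost is wording in two sections and in the pharmacokinetic analysis. No samples or new eCRF fields are needed, since the cards already hold the evening times. The drawback is that AUC0-8 covers only part of the 12 h interval: in the worked case 6.852/8.647 = 79% of AUC0-12.
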